4 PARTICIPANT ENTRY

4.1 INCLUSION CRITERIA FOR MAIN TRIAL:

- · Aged 18 years or older
- · Previously taken one or more statins
- Withdrawn from statins because of perceived side effects
- Developed side effects within 2 weeks of initiation
- Clinical indication for statins for primary or secondary prevention of cardiovascular disease or dyslipidaemia

4.2 EXCLUSION CRITERIA FOR MAIN TRIAL:

- History of any condition that causes chronic pain
- History of severe mental illness (as their experience of symptoms may already be altered)
- Current taking fibrates (because of the risk of interaction with statins but will not exclude participants taking ezetimibe).
- History of statin intolerance with creatine kinase elevation greater than 5 times the upper limit of normal
- History of statin intolerance with anaphylaxis
- History of statin intolerance with myalgia and rise in serum creatine kinase

Confidential Page 8 of 22

Version 1.4 10th April 2020

- History of statin intolerance with rhabdomyolysis
- History of statin intolerance with liver function abnormalities, defined as aspartate aminotransferase (AST) or alanine aminotransferase (ALT) >3 times the ULN
- · Currently taking antiretrovirals with known interaction to statins
- Currently taking any drug other than antiretrovirals with known interaction to statins
- · Pregnant or breast feeding
- Side effects taking longer than 2 weeks to present (because in such participants much longer blocks of treatment would be required, if the present study is positive such studies will be planned for the future)*
- In clinical judgement of study doctor, participant should not be enrolled on the study

*All participants excluded for this reason will be logged so that the proportion excluded will be known. The study will be explained to consecutive eligible participants, and those giving informed consent will be recruited.

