4.3 Contraindications

Atorvastatin is contraindicated in patients:

- with hypersensitivity to the active substance or to any of the excipients listed in section 6.1
- with active liver disease or unexplained persistent elevations of serum transaminases exceeding 3 times the upper limit of normal
- during pregnancy, while breast-feeding and in women of child-bearing potential not using appropriate contraceptive measures (see section 4.6).
- treated with the hepatitis C antivirals glecaprevir/pibrentasvir

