4.6 Fertility, pregnancy and lactation

Women of childbearing potential

Women of child-bearing potential should use appropriate contraceptive measures during treatment (see section 4.3).

Pregnancy

Atorvastatin is contraindicated during pregnancy (see section 4.3). Safety in pregnant women has not been established.

Confidential Page 46 of 22

46 of 67

SAMSON Protocol No: 1.4

Version 1.4 10th April 2020

No controlled clinical trials with atorvastatin have been conducted in pregnant women. Rare reports of congenital

anomalies following intrauterine exposure to HMG-CoA reductase inhibitors have been received. Animal studies have

shown toxicity to reproduction (see section 5.3).

Maternal treatment with atorvastatin may reduce the fetal levels of mevalonate which is a precursor of cholesterol

biosynthesis. Atherosclerosis is a chronic process, and ordinarily

discontinuation of lipid-lowering medicinal products

during pregnancy should have little impact on the long-term risk associated with primary hypercholesterolaemia.

For these reasons, atorvastatin should not be used in women who are pregnant, trying to become pregnant or suspect

they are pregnant. Treatment with atorvastatin should be suspended for the duration of pregnancy or until it has been

determined that the woman is not pregnant (see section 4.3.)

Breast-feeding

It is not known whether atorvastatin or its metabolites are excreted in human milk. In rats, plasma concentrations of

atorvastatin and its active metabolites are similar to those in milk (see section 5.3). Because of the potential for serious

adverse reactions, women taking atorvastatin should not breast-feed their infants (see section 4.3). Atorvastatin is

contraindicated during breastfeeding (see section 4.3).

Fertility

In animal studies atorvastatin had no effect on male or female fertility (see section 5.3).

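### Protocol 4.2 is narrower than the atorvastatin contraindications appended to the same protocol, and protocol 4.3 names no stop for pregnancy

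*Protocol*

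**What the plan says.** Two parts of the protocol deal with who should not take atorvastatin. Both the protocol and the appended product text have a section numbered 4.3, so each is named in full here.

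**Protocol 4.2 (exclusion criteria for the main trial).** On pregnancy the criterion is "Pregnant or breast feeding". On the liver it is "History of statin intolerance with liver function abnormalities, defined as aspartate aminotransferase (AST) or alanine aminotransferase (ALT) >3 times the ULN". The list ends with a general line: "In clinical judgement of study doctor, participant should not be enrolled on the study".

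**Protocol 4.3 (withdrawal criteria).** It gives one reason to withdraw: the participant chooses to go back on clinical statin treatment.

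**Product text in Appendix Four, section 4.3 (contraindications).** Besides pregnancy and breast feeding, atorvastatin is contraindicated "in women of child-bearing potential not using appropriate contraceptive measures". On the liver it is contraindicated in patients "with active liver disease or unexplained persistent elevations of serum transaminases exceeding 3 times the upper limit of normal".

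**Product text in Appendix Four, section 4.6.** "Women of child-bearing potential should use appropriate contraceptive measures during treatment". It adds: "Treatment with atorvastatin should be suspended for the duration of pregnancy".

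**The concern.** Each participant is scheduled to take atorvastatin 20 mg, blinded, in four of twelve months. The eligibility list is the written rule that decides who may do so. In two places it states part of a contraindication and leaves out the rest, although the full wording is in the protocol's own appendix. Followed as written, it does not require exclusion of a woman of child-bearing potential who uses no contraception, or of a patient whose active liver disease has nothing to do with an earlier statin.

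The gap continues after entry. Pregnancy, contraception and liver status can all change over twelve months, and protocol 4.3 gives no instruction for any of them. What is at stake is participant safety. The sample size, the error rate and the nocebo estimate are not involved.

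**Working it through.** The plan gives no figure to reproduce on this point, so the main check sets the texts side by side.

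**Step 1: product text 4.3 against the specific criteria of protocol 4.2.**

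- *Hepatitis C antivirals.* Covered by the 4.2 line on drugs with a known interaction with statins.
- *Pregnancy and breast feeding.* Covered.
- *Child-bearing potential without appropriate contraception.* Not covered. Protocol 4.1 admits adults from 18 years, with no upper age limit and no restriction by sex, so such women can enter.
- *Active liver disease.* Not covered.
- *Unexplained persistent transaminases above 3 times the upper limit.* Covered only if the rise was part of an earlier statin intolerance. A rise from another or unknown cause meets no specific criterion.
- *Hypersensitivity.* Covered in part: 4.2 names statin intolerance with anaphylaxis, while the product text says "with hypersensitivity to the active substance or to any of the excipients listed in section 6.1". This is secondary to the pregnancy and liver gaps.

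**Step 2: events after entry.** Product text 4.6 asks for contraception during treatment and for suspension in pregnancy. Protocol 4.3 contains no stop for pregnancy, for loss of contraception or for liver disease.

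**Step 3: would another written step require the exclusion or the stop?**

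- The study doctor's interview and suitability decision (protocol 3.3 and 7) depend on judgement and name neither condition.
- Protocol 6.1 keeps the product summary in the trial master file and has it reviewed at least annually. It does not make the contraindications into eligibility rules.
- Unscheduled calls (protocol 7) follow severe discomfort or missing scores. Early pregnancy or silent liver disease need cause neither.
- Screening in protocol 7 and the visit schedule in SAP 3.1 list no pregnancy or liver function test.

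**Step 4: who can still benefit.** SAP 4.1, in a plan dated 14 January 2020, reports 60 randomised against a target of 50. Protocol 1.4 is dated 10 April 2020. A change to 4.2 therefore probably reaches few or none. A rule for participants still being dosed could reach some. Version 1.4 allows the end of study visit by telephone during the pandemic, which suggests, but does not prove, that some had not yet reached month 12.

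**Step 5: cost to Hypothesis 1.** SAP 6.2.1 divides completers by enrolled participants. Taking the 60 randomised as enrolled, one further non-completer lowers the proportion by 1/60 = 0.0167, or 1.7 percentage points. A patient excluded at screening is not in the denominator and changes it by 0.

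**The case against.** The strongest reply is that the contraindications are already in the protocol, because the product text is one of its appendices. The study doctor takes a medical history, decides suitability and has an express power to exclude. Entry also requires previous statin use and a clinical indication, all adverse events are reported, participants may withdraw at any time, and a monitoring committee reviews safety annually. Repeating each label line as a criterion could then be called a drafting preference.

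Much of this stands, and it is why the severity is low. It does not close the point. The judgement line permits exclusion but does not require it, and the protocol did not rely on it for pregnancy, fibrates or raised AST and ALT, which it lists. Previous statin use shows a past prescription, not present contraception or liver status.

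Two further objections are accepted. A history question finds only known liver disease, so an unrecognised transaminase rise would still be missed. And suspending a drug is a dosing action, whereas protocol 4.3 concerns leaving the trial, so the fix must keep the two apart.

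A reader might infer that contraindicated patients were enrolled or harmed. The documents do not show this: they give no count of such patients. A reader might also infer that contraception advice was never given. That cannot be concluded, because consent pages were removed and the information sheets are not supplied.

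**Conclusion.** The point holds as a low-severity safety improvement, limited to protocol 4.2 and protocol 4.3. Section 4.2 lacks a criterion on contraception, and one on active liver disease or unexplained persistent transaminase elevation unrelated to past statin intolerance. Protocol 4.3 names no stop for pregnancy, although the appended text asks for suspension. Confidence is high on the comparison of texts and much lower on any practical consequence, since the number of participants affected is unknown and may be zero.

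The conclusion assumes that no other protocol text makes these exclusions mandatory, and none was found in what is supplied. It does not extend to the galactose disorders in product text 4.4, which are a warning and not a contraindication. No bias in the nocebo ratio follows, and none is claimed.

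**What to change.** **For participants still being dosed.** Ask about pregnancy, contraception and active liver disease at the existing monthly nurse call. Add to protocol 4.3 that study tablets are stopped if pregnancy occurs or a contraindication applies. Apply the rule to statin and placebo alike, so that no unblinding is needed. State that stopping tablets is not withdrawal, and that the participant may stay in follow-up and symptom scoring.

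**For anyone still to be enrolled (possibly nobody).** Add to protocol 4.2, checked by history at screening: child-bearing potential without appropriate contraception; and active liver disease or known, unexplained, persistent transaminases above 3 times the upper limit of normal.

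**Cost.** A short amendment, a few history questions and no new test. A few participants may stop tablets. Each lowers Hypothesis 1 completion by the 1/60 shown above, and only if counted as a non-completer, so the amendment should say how they are counted. Under SAP 6.1.1 such a participant still enters the primary analysis if each of the three treatments has at least one month with at least 10 daily scores. The SAP gives no rule for scores recorded in assigned tablet months after a stop, so the amendment should supply one.

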4.3 WITHDRAWAL CRITERIA

If during the study, participants choose to re-start clinical statin therapy, they will withdraw from the study and start open medication.

4.4 UNBLINDING PROCEDURE

In the unlikely event unblinding is necessary it will be possible for the Chief Investigator to quickly and easily unblind to treatment using the unblinding function of the trial database. A back-up unblinding list will be held at the pharmacy.

5 PHARMACOVIGILANCE

5.1 DEFINITIONS

Adverse Event (AE): any untoward medical occurrence in a patient or clinical trial subject administered a medicinal product and which does not necessarily have a causal relationship with this treatment. An AE can therefore be any unfavourable and unintended sign (including an abnormal laboratory finding), symptom or disease temporarily associated with the use of an investigational medicinal product (IMP), whether or not considered related to the IMP.

Adverse Reaction (AR): all untoward and unintended responses to an IMP related to any dose administered. All AEs judged by either the reporting investigator or the sponsor as having reasonable causal relationship to a medicinal product qualify as adverse reactions. The expression reasonable causal relationship means to convey in general that there is evidence or argument to suggest a causal relationship.

Unexpected Adverse Reaction: an AR, the nature or severity of which is not consistent with the applicable product information (summary of product characteristics). When the outcome of the adverse reaction is not consistent with

Confidential Page 9 of 22

SAMSON Protocol No: 1.4

Version 1.4 10th April 2020

the applicable product information this adverse reaction should be considered as unexpected. Side effects documented in the summary of product characteristics which occur in a more severe form than anticipated are also considered to be unexpected.

Serious Adverse Event (SAE): any untoward and unexpected medical occurrence or effect that:

- Results in death
- Is life-threatening refers to an event in which the participant was at risk of death at the time of the event; it does not refer to an event which hypothetically might have caused death if it were more severe.
- Requires hospitalisation, or prolongation of existing inpatients' hospitalisation
- Results in persistent or significant disability or incapacity
- · Is a congenital anomaly or birth defect
- Medical judgement should be exercised in deciding whether an AE is serious in other situations. Important AEs that are not immediately life-threatening or do not result in death or hospitalisation but may jeopardise the subject or may require intervention to prevent one of the other outcomes listed in the definition above, should also be considered serious.

Suspected Unexpected Serious Adverse Reaction (SUSAR): any suspected adverse reaction related to an IMP that is both unexpected and serious.

5.2 CAUSALITY

Most adverse events and adverse drug reactions that occur in this study, whether they are serious or not, will be expected treatment-related toxicities due to the drugs used in this study. The assignment of the causality should be made by the investigator responsible for the care of the participant using the definitions in the table below.

If any doubt about the causality exists other clinicians may be asked to advise in some cases.

In the case of discrepant views on causality between the investigator and others, all parties will discuss the case. In the event that no agreement is made, the MHRA will be informed of both points of view.

Relationship	Description		
Unrelated	There is no evidence of any causal relationship		
Unlikely There is little evidence to suggest there is a causal relations (e.g. the event did not occur within a reasonable time a administration of the trial medication). There is another reasonable explanation for the event (e.g. the participal clinical condition, other concomitant treatment).			
Possible There is some evidence to suggest a causal relation because the event occurs within a reasonable administration of the trial medication). However, the other factors may have contributed to the event			

Confidential Page 10 of 22

SAMSON Protocol No: 1.4

Version 1.4 10th April 2020

	participant's clinical condition, other concomitant treatments).		
Probable	There is evidence to suggest a causal relationship and the		
	influence of other factors is unlikely.		
Definitely There is clear evidence to suggest a causal relationship a			
	other possible contributing factors can be ruled out.		
Not There is insufficient or incomplete evidence to make a clini			
assessable judgement of the causal relationship.			

5.3 REPORTING PROCEDURES

There is only one study site and the principal investigator is also the chief investigator of the study. All adverse events will be reported. Depending on the nature of the event the reporting procedures below should be followed. Any questions concerning adverse event reporting will be directed to the Chief Investigator in the first instance. A flowchart is given below to aid in the reporting procedures.

5.3.1 Non serious adverse reactions/adverse events

All such toxicities, whether expected or not, should be recorded in the toxicity section of the relevant case report form

5.3.2 SERIOUS ADVERSE REACTIONS/ADVERSE EVENTS

Fatal or life threatening SAEs and SUSARs should be reported on the day that the site is aware of the event. The SAE form asks for the nature of event, date of onset, severity, corrective therapies given, outcome and causality (i.e. unrelated, unlikely, possible, probably, definitely). The responsible investigator should sign the causality of the event. Additional information should be gained within 5 days if the reaction has not resolved at the time of reporting.

5.3.3 SERIOUS ADVERSE EVENTS

An SAE form should be completed by the site within 24 hours. However, hospitalisations for elective procedures of a pre-existing condition do not need reporting as SAEs.

All SAEs should be reported to the <name of REC> where in the opinion of the Chief Investigator, the event was:

- 'related', ie resulted from the administration of any of the research procedures; and
- 'unexpected', ie an event that is not listed in the protocol as an expected occurrence

5.3.4 Suspected unexpected serious adverse reactions

[figure not shown]
In the case of suspected unexpected serious adverse reactions, the staff at the site should:

Confidential Page 11 of 22

SAMSON Protocol No: 1.4

Version 1.4 10th April 2020

Complete the SAE case report form and send it immediately (within 24 hours, preferably by fax), signed and dated to the MHRA, REC and sponsor together with relevant treatment forms and anonymised copies of all relevant investigations. The study team will notify the MHRA, REC and sponsor of all SUSARs occurring during the study according to the following timelines; fatal and life-threatening within 7 days of notification and non-life threatening within 15 days. All local investigators will be informed.

6 IMP MANAGEMENT AND ACCOUNTABILITY

6.1 MANAGEMENT/SUPPLY OF IMPS

An up-to-date summary of product characteristics (SmPC) of Atorvastatin will be included in the Trial Master File (TMF), which will be reviewed at least annually and any change should be notified and an updated SmPC added to the TMF.

Research staff will be delegated IMP management responsibilities by the CI. The CI in conjunction with research staff delegated IMP management responsibilities must:

- a. Maintain records that document shipment, receipt handling, return and destructions of the IMP
- b. Maintain a system for retrieving IMPs and documenting this retrieval (e.g. for deficient product recall, reclaim after trial completion, expired reclaim).
- Maintain a system for the handling of unused IMP(s) and for the documentation of returned IMPs

Confidential Page 12 of 22

SAMSON Protocol No: 1.4

Version 1.4 10th April 2020

 Maintain records of batch sample analyses, characteristics and storage conditions, e.g. temperature logs.

6.2 DRUG ACCOUNTABILITY

Drug accountability logs will be kept for dispensing IMP and for reconciling returned medication. The accountability log will detail:

- Subject identification code
- · Date dispensed
- Dose
- Date of expiry
- · Quantity dispensed
- · Batch number
- Date returned
- Quantity returned
- Recorder's initials

All IMPs should be stored and dispensed by the delegated research staff and managed to the same standards as licensed medicines.

6.3 LABELLING

The IMP (atorvastatin 20mg OD or placebo) will be labelled, to ensure all supplies are in consistent packaging with consistent labelling to maintain blinding. They will be labelled with:

- i. The name of the investigator
- ii. Sponsor:
- iii. Product name, form and strength or placebo
- iv. Date of supply
- v. Name and address of site
- vi. Trial specific code
- vii. Code for the trial subject
- viii. Directions (as specified)
- ix. "Keep out of reach of children"

As it is a blinded trial, the coding system for the investigational product includes a mechanism that permits rapid identification of the product in the unlikely case of a medical emergency.

6.4 TRIAL SPECIFIC SOPS

The CI, in conjunction with the research staff at the site should ensure that the following trial specific SOPs are in place before starting the trial:

- Receipt and recording of safe delivery of IMPs
- Safe Handling and storage of IMPs
- Code Breaking
- Preparation and dispensing of IMPs
- Return and disposal of unused IMPs
- Maintaining a pharmacy study file

Confidential Page 13 of 22

SAMSON Protocol No: 1.4

Version 1.4 10th April 2020

7 ASSESSMENT AND FOLLOW-UP

Participants will attend a screening visit where the study doctor will receive written informed consent from them if they decide to participate. Then the study doctor will assess the participants eligibility for the study by evaluating their past medical history and previous statin intolerance. Participant's blood pressure will also be measured and if a participant does not have a recent lipid profile recorded in the last 12 months, they will be offered the option of having one undertaken as part of the screening visit. The study doctor will determine if the participant is suitable to be enrolled in the study. If suitable, they will be enrolled on inform.

Unscheduled assessments will not be performed unless participants develop adverse events which the chief investigator considers 'related' to the trial procedure or Atorvastatin therapy.

Scheduled follow-up telephone calls will be undertaken during every month during the 12-month period of the trial. Furthermore, participants scoring will be monitored by study nurse and if they show severe discomfort or if participants are not scoring on their phone unscheduled telephone follow-up calls will be made and if required a unscheduled study visit to see the study doctor and perform unscheduled tests as deemed necessary by the study doctor.

End of study will be defined as when the specified number of patients have been recruited, all patients have completed the 18-month phone interview and the database is locked.

The 12-month follow-up contact may be combined with the end of study visit, if so this would be a face-to-face visit at the study centre or by telephone if the participant is unable to attend in-person during the COVID pandemic. The end of study visit may take place up to 31 days after the 12-month telephone follow-up.

